#### **Screening Visit:**

- Obtain and document signed Informed Consent document and HIPAA Authorization.
- Review past medical history in Armed Forces Health Longitudinal Technology Application (AHLTA) to verify the inclusion/exclusion criteria including previous encounter, vital signs review, co-morbidities, demographics, problems list, confirmatory x-rays demonstrating radiographic evidence of knee osteoarthritis.
- We will ask the participants to complete the Screening Visit Medical history questionnaire.
- Record: Age at time of randomization, gender, Kellgren and Lawrence (KL) Grade score at time of enrollment, age at time of osteoarthritis diagnosis, prior knee osteoarthritis therapies to date, name of standard of care medications (over-the-counter and prescription), current email address (to be used for scheduling and weekly email reminders), height (in inches), weight (in pounds), history of prior injury to the affected knee(s), current level of exercise, physical therapy in the past year, and prior experience with mindfulness.

**Randomization:** Subjects will be randomized into 1 of 2 groups using block randomization with repeated measures:

- **Intervention Group:** Patient education regarding osteoarthritis, its natural history, and common treatments plus the mindfulness (intervention) app. They will be provided with a pre-paid 12-week subscription to the mindfulness application, and provided an in-person demonstration on how to use it, and the subscription license code will be recorded for the purposes of tracking use after the conclusion of the study. The intervention group will be asked to use the mindfulness app 10 minutes per day/5 days per week. To standardize Pack usage across all participants, users will be asked to complete the Headspace Essentials", "Pain Management", and "Physical Health" Session Packs.

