## 6. DATA ANALYSIS

### Data Analysis:

### Outcome Measures:

To compare the effect of the mindfulness app intervention against the control: using an intention-to-treat paradigm, the two groups will be compared via one-way analysis of variance (ANOVA).

To compare the effect of a mindfulness app intervention among high and low strata of baseline pre-intervention SF-12 and FFMQ-15 scores: statistical calculation is based on the interaction effect in a 2-way analysis of variance (ANOVA) model with 5% two-sided significance level.

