### Sample Size Estimation/Power Analysis:

Based on the KOOS Minimal Detectable Changes in patients with knee OA of 10 with a Standard Deviation of 15, a sample size of 74 per group will have 80% power to detect such a difference based on Student's t test for independent samples with 5% two-sided significance level. Allowing for 25% dropout, the required sample size is 99 per group to accomplish the first aim.

However, to determine if high or low strata of baseline mindfulness affects pain outcomes, a sample size of 144 per group (72 in each SF12 stratum) will have 80% power to detect a difference of 10 points with a standard deviation of 15 points (i.e., no mindfulness effect in the high SF12 stratum vs. a 10-point mindfulness effect in the low SF12 stratum). Allowing for the aforementioned 25% dropout rate, we anticipate 180 participants per group or 360 total participants.

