### Number of Subjects:

	# Planned to Enroll	# Enrolled	# Planned to Complete Study	TOTAL
Number of Subjects at Scott AFB	120	0	96	360
Number of Subjects at Travis AFB	120	0	96	
Number of Subjects at Nellis AFB	120	0	96	

*\*If any location recruits more subjects, they will be allowed to continue recruiting not to exceed the total number of subjects for all locations.*

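### Enrolling 360 does not cover the stated 25% dropout: 135 per group would remain, not the 144 needed for 80% power on the interaction aim that sets the trial's size

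*Combined protocol and SAP*

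**What the plan says.** All the figures are in section 6, Data Analysis, of the combined protocol and SAP.

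- **First aim** (Sample Size Estimation/Power Analysis). The plan takes 74 evaluable per group and states: "Allowing for 25% dropout, the required sample size is 99 per group to accomplish the first aim".
- **Second aim** (same section). The plan calls for "a sample size of 144 per group (72 in each SF12 stratum"), which it says "will have 80% power to detect a difference of 10 points with a standard deviation of 15 points". The alternative is "no mindfulness effect in the high SF12 stratum vs. a 10-point mindfulness effect in the low SF12 stratum". Under Outcome Measures, the "statistical calculation is based on the interaction effect in a 2-way analysis of variance (ANOVA) model with 5% two-sided significance level".
- **Enrolment for the second aim** (same section). "Allowing for the aforementioned 25% dropout rate, we anticipate 180 participants per group or 360 total participants".
- **Number of Subjects table.** The row "Number of Subjects at Scott AFB" gives 120 to enrol and 96 to complete. The Travis and Nellis rows give the same figures, and the total is 360. The footnote lets a site recruit beyond its share, but not beyond the overall total.

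**The concern.** The word *aforementioned* ties the second aim to the same 25% used for the first, yet the two enrolment figures cannot come from the same calculation at that rate. The first aim divides by 0.75. The second arrives at 180, which is 144 × 1.25. Adding 25% to the evaluable number does not offset losing 25% of the enrolled number.

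The second aim sets the trial's size, since by the plan's own figures the first needs only 99 per group. Any error in its inflation therefore goes straight into the 360. The number of completers also matters for the analysis. Under the Visit 5 heading, participants who do not answer three reminders are removed and not queried again. Under Statistical Analysis, those with omitted KOOS data count as dropouts, and no imputation is described. Because the footnote caps enrolment at the total, over-recruitment cannot make up the difference.

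**Working it through.** **Inputs, all from section 6.** Two-sided alpha 0.05; interaction contrast 10 − 0 = 10 points; SD 15; two groups by two equal strata; 144 evaluable per group (m = 72 per cell); dropout 25%; 180 enrolled per group. Equal allocation is inferred from the equal group sizes.

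**1. Reproduce the 144.** For a 2×2 interaction contrast with m per cell:

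- SE = SD × √(4/m)
- noncentrality = (10/SE)² = 100m/(225 × 4) = m/9, tested by F on 1 and 4m − 4 degrees of freedom

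At m = 72, the noncentrality is 8.0 on 284 df and power is 80.5%. At m = 71, power is 79.9%. So 72 per cell, or 144 per group, is exactly the minimum by the F test, and the plan's base figure is correct. The normal approximation gives a minimum of 4 × (15 × (1.960 + 0.842)/10)² = 70.6, so 71 per cell or 142 per group, with 80.7% power at m = 72.

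**2. Check the inflation.**

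| Calculation | Result per group |
|---|---|
| First aim, 74/(1 − 0.25) | 98.7, so 99 (matches the plan) |
| First aim, 74 × 1.25 | 92.5 (does not match) |
| Second aim, 144/(1 − 0.25) | 192 (does not match) |
| Second aim, 144 × 1.25 | 180 (matches) |
| Second aim, 144/(1 − 0.20) | 180 (also matches) |

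At 25% dropout the requirement is 2 × 192 = 384 in total, which is 24 more than 360.

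**3. What 360 delivers at 25% dropout.** 180 × 0.75 = 135 per group, or 135/2 = 67.5 per cell and 270 in total. The noncentrality is 67.5/9 = 7.5 on 4 × 67.5 − 4 = 266 df.

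| Completers per group | Per cell | Power, noncentral F | Power, normal |
|---|---|---|---|
| 144 (as planned) | 72 | 80.5% | 80.7% |
| 135 (25% loss from 180) | 67.5 | 77.9% | 78.2% |

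**4. Compare with the enrolment table.** 3 × 96 = 288 completers of 360, and 1 − 96/120 = 20% loss. 288/2 = 144 per group, so the table agrees with the power calculation only at 20%. At 25%, each site would have 120 × 0.75 = 90 completers, 270 in all.

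**5. Sensitivity to the strata.** The figures above use the plan's equal strata. For unequal strata of sizes a and b per group, SE = 15 × √(2/a + 2/b). With 135 per group, an assumed 40/60 split (54 and 81) gives about 76.5% and an assumed 30/70 split about 70.9%, against 78.2% for 50/50 (all by normal approximation).

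**The case against.** The arithmetic cannot be disputed, but four points on cause and weight deserve a hearing.

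- **The 180 may come from a correct division at 20%.** 144/0.80 is also 180, and the table plans exactly 20% loss. The documents do not show how 180 was obtained, so this reading is open. It does not remove the problem: the 25% attached to the second aim would then be the wrong figure, and the text would still need correcting.
- **The loss of power is small.** Power ends 2.1 points below 80% by the F test and 1.8 by the normal approximation. That is right, and this should not be presented as a seriously underpowered trial.
- **The comparison of the app with control is not at risk.** With 135 per group, a 10-point difference at SD 15 has t-test power above 99%. Only the interaction aim is affected. The plan calls that aim secondary in the Background and a second primary aim under Statistical Analysis.
- **Unequal strata could matter more than dropout.** A 30/70 split would cost more power than the inflation error. This also stands. The plan gives no SF-12 cut-point, so any restated power should carry the equal-strata condition.

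**Conclusion.** The concern holds. The 25% dropout, the 360 enrolled and the 288 planned completers cannot all be true. At the plan's stated rate, 360 enrolled yields 270 completers, 18 fewer than the table shows and 9 per group fewer than the power calculation needs. Interaction power is then 77.9% rather than 80.5%, a loss of about 2.6 points. There is no slack to absorb it, because 72 per cell is the exact minimum for 80%.

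This rests on the plan's own effect size, SD and alpha, on equal allocation and equal strata, and on dropout spread evenly over the four cells. The internal contradiction is certain, the effect on power is modest, and the first aim is not endangered.

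**What to change.** Choose one dropout rate, apply n/(1 − d) to both aims, and make the sample size text and the Number of Subjects table agree. With 360 enrolled there are two ways to do this:

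1. **Adopt 20%.** Change the rate in the sample size text and give a reason for it, so that it is not simply lowered to fit the total. The table stays as it is. If 20% is used throughout, the first-aim figure becomes 74/0.80 = 92.5, so 93 per group instead of 99, taking the 74 as given.
2. **Keep 25%.** Change the table to 90 completers per site (270 in total) and restate second-aim power as about 78%, conditional on equal SF-12 strata.

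Both are text and table corrections with no extra participants. The cost is a thinner dropout margin in the first case and a slightly lower stated power in the second. Without support for 20%, the second is the more candid choice.

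If the sponsor wants to keep both 25% dropout and 80% power, enrolment must rise to 192 per group. That is 384 in total, or 384/3 = 128 per site, of whom 128 × 0.75 = 96 would complete. It costs 24 more participants and a higher enrolment cap.

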### Statistical Analysis:

Using an intention-to-treat paradigm, the first primary aims will be statistically compared via one-way analysis of variance (ANOVA). The second primary aim will be statistically compared via two-way analysis of variance (ANOVA).

Missing primary outcome data will be acknowledged in the overall report of analysis. The primary outcome data is based on KOOS scoring system. Per the validated instructions of KOOS analysis, "as long as at least 50% of the subscale items are answered for each subscale, a mean score can be calculated. If more than 50% of the subscale items are omitted, the response is considered invalid and no subscale score should be calculated." In the event that the KOOS data is omitted, the participant will be regarded as a "drop out" and they will be included as such in the intent-to-treat analysis.

Subgroup analyses will be completed via 2-way ANOVA, stratified by FFMQ-15 and SF-12 scores. Subgroup analysis based on age, gender, comorbid behavioral health conditions, and duration of Knee OA symptoms may be considered.

Over-the-counter pharmacologic treatment of musculoskeletal pain is a common practice; given the near ubiquitous usage of these medications, this protocol does not preclude use of NSAIDs or acetaminophen. However, medication use will be monitored via weekly surveys and analyzed post-hoc as a potential confounder of the collected data.

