**2. RESEARCH PLAN**

Purpose of Study:
This study will investigate if mindfulness training via a smartphone mobile app is effective in improving OA-related knee pain.
Hypotheses, Research Questions, or Objectives:

 
• Objective 1: Test whether use of a mindfulness mobile app improve knee pain in adults with knee OA among active duty and other DoD beneficiaries.
 
• Objective 2: Evaluate if self- reported, health-related quality of life and mindfulness scores predict response to mindfulness treatment in OA.
 
• Null Hypothesis 1: A mindfulness mobile app has no effect on knee pain in adults with knee OA.
 
• Alternative Hypothesis 1: A mindfulness mobile app improves knee pain in adults with knee OA.
 
• Null Hypothesis 2: Self- reported, health-related quality of life and mindfulness scores have no effect on response to mindfulness treatment in OA.
 
• Alternative Hypothesis 2: Self- reported, health-related quality of life and mindfulness scores predict response to mindfulness treatment in OA.
 

Significance:
Osteoarthritis (OA) is a major cause of disability in the United States and is expected to affect 26% of Americans by 2040  . Studies of the socioeconomic burden of OA demonstrate a 2-4 fold increase in healthcare expenditures for people with OA as compared to non-affected controls  . In addition, associated healthcare costs continue to rise: recent estimates of insurer and out of pocket healthcare costs of osteoarthritis exceed \$185 billion USD per year with another \$10 billion lost from absenteeism at work  .

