To date, mindfulness studies involving chronic pain conditions have involved manpower- intensive interventions (in-person mindfulness training, group therapy, multiple physician appointments, etc.), which are difficult to implement in busy clinical settings. Web- and mobile health applications (mHealth) may provide an effective alternative to these interventions. A 2016 systematic review of 10 web-based mindfulness training programs found that such facilitator- free interventions were effective in reducing depression and anxiety. To our knowledge, only one protocol to date has been published investigating the use of a mindfulness mobile app as an intervention for improving outcomes in chronic pain.

Our primary aim in this study is to determine if regular use of a mindfulness application improves pain outcomes in adults with knee osteoarthritis. Our secondary aim is to determine if self-reported Healthcare-Related Quality of Life (HRQoL) scores predict response to mindfulness treatment in OA. We hypothesize that the use of an mHealth intervention for mindfulness training may be an effective adjunct treatment of chronic knee osteoarthritis pain; specifically, that regular use of a mindfulness application will result in a statistically significant reduction in pain outcomes and improvement in physical function as determined by the KOOS scoring system. We also hypothesize that those with lower baseline self-reported HRQoL scores are more likely to see a greater improvement in their pain and function with use of a mindfulness application than those with higher baseline scores.

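### The moderator question is secondary in the Background but a second primary aim in the Statistical Analysis, so the plan can be read as allowing two primary tests with no multiplicity rule

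*Combined protocol and SAP*

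**What the plan says.** The rank of the two aims depends on the section read.

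- **Section 2, Background and Review of Literature.** One primary aim: "Our primary aim in this study is to determine if regular use of a mindfulness application improves pain outcomes in adults with knee osteoarthritis". The moderator question follows as secondary: "Our secondary aim is to determine if self-reported Healthcare-Related Quality of Life (HRQoL) scores predict response to mindfulness treatment in OA".
- **Section 2, Hypotheses, Research Questions, or Objectives.** Two numbered objectives, each with its own null hypothesis, and no statement that one outranks the other. Objective 2 reads "Evaluate if self- reported, health-related quality of life and mindfulness scores predict response to mindfulness treatment in OA", so it covers mindfulness scores as well as quality of life.
- **Section 6, Statistical Analysis, first paragraph.** Both aims are primary: "the first primary aims will be statistically compared via one-way analysis of variance (ANOVA"), and then "The second primary aim will be statistically compared via two-way analysis of variance (ANOVA").
- **Same section, two paragraphs later.** "Subgroup analyses will be completed via 2-way ANOVA, stratified by FFMQ-15 and SF-12 scores".

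On significance levels, Outcome Measures says of the interaction that the "statistical calculation is based on the interaction effect in a 2-way analysis of variance (ANOVA) model with 5% two-sided significance level". The level for Aim 1 appears only in the sample-size text: "80% power to detect such a difference based on Student's t test for independent samples with 5% two-sided significance level". Outcome Measures and Statistical Analysis name the one-way ANOVA for Aim 1 without a level.

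Section 3a (Interventions and Observations) names one primary outcome measure, change in the KOOS pain subscale.

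**The concern.** The rank of an analysis decides what the trial may claim. Suppose the overall app effect is not significant but the app-by-stratum interaction is. Under the Statistical Analysis section the sponsor could report success on a primary aim. Under the Background section the same data give a failed primary aim and a secondary finding. With both texts in force, the choice could be made after the results are known.

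The label is not a stray word on a minor analysis. The moderator test sets the size of the trial: the sample-size section asks for 99 per group for Aim 1, then raises this to 180 per group for the interaction. A reader who sees which test drives the sample size could reasonably take it as primary.

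**Working it through.** **1. Do the sections reconcile?** The Background ranks the aims primary and secondary. The Statistical Analysis ranks them first primary and second primary. The Objectives give no rank. The single primary outcome in section 3a does not settle it, because both aims are tested on pain: the interaction is powered for a 10-point mindfulness effect in one SF-12 stratum against none in the other. No section gives a hierarchy, split or gatekeeping rule.

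**2. The plan's own figure for the interaction.** Inputs from the sample-size section: difference of 10 points, SD 15, 80% power. Two-sided 5% is from Outcome Measures.

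- n per cell = 4 × [SD × (z₀.₉₇₅ + z₀.₈₀) / difference]² = 4 × [15 × (1.960 + 0.842) / 10]² = 70.6, so 71.
- With the noncentral t distribution on 4n − 4 degrees of freedom: 72 per cell, power 80.5%.
- 72 × 2 strata = 144 per group, which is the stated figure.

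So the interaction was sized at a full 5%, with nothing reserved for a second primary test.

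**3. Error rate if both tests are primary.** In a balanced two-by-two layout the overall app effect and the interaction are orthogonal contrasts, so the tests are close to independent. When neither effect exists:

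- P(at least one false claim) = 1 − (1 − 0.05)² = 1 − 0.9025 = 9.75%.
- A simulation of 100,000 null trials with 72 per cell gave 9.8%.
- The upper bound without independence is 0.05 + 0.05 = 10%.

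This counts one interaction test. Outcome Measures names two moderators, SF-12 and FFMQ-15; three independent tests in all would give 1 − 0.95³ = 14.3%.

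**4. Error rate if only Aim 1 is primary.** One primary test at 5%. The efficacy claim, taken alone, has this 5% rate under either reading.

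**5. Cost of testing Aim 2 only after Aim 1 succeeds.** Under the plan's pattern (0 points in the high stratum, 10 in the low) the average app effect is (0 + 10) / 2 = 5 points.

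- Standard error of the overall effect with 144 per group: 15 × √(2/144) = 1.77, so 5 / 1.77 = 2.83.
- Standard error of the interaction with 72 per cell: 15 × √(4/72) = 3.54, so 10 / 3.54 = 2.83.
- The standardised effects are equal, so each test has about 80.5% power.
- P(both significant) ≈ 0.805 × 0.805 = 65%.

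A 40,000-run simulation using the one-way ANOVA for Aim 1 gave 63.5%; that test has slightly lower power, about 79%, because it leaves the stratum difference in the error term.

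**The case against.** **The Background already gives the intended order.** It names one primary aim, and section 3a names one primary outcome. A reader might infer from the Statistical Analysis wording that the trial simply has two primary 5% tests. The documents do not support that as a flat statement; they permit the reading in one section and contradict it in another. This part of the objection stands.

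**The subgroup label is not a third rank.** It is tempting to say the moderator analysis carries three conflicting labels. But subgroup describes a type of analysis: a two-way ANOVA by baseline SF-12 and FFMQ-15 can be a subgroup analysis and either primary or secondary. The contradiction is between two labels, primary and secondary.

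**The 9.75% is not a breach of a stated limit.** The plan never states a family-wise 5%. It gives per-test levels, and the one for Aim 1 only in the sample-size text. A reader might infer that the false-positive rate for app efficacy nearly doubles. It does not: the two nulls are separate, and rejecting the moderation null does not reject the efficacy null. The 9.75% is the rate of any false primary claim, and it matters only if a positive interaction may be presented as trial success. That also stands, but the Statistical Analysis wording allows exactly that presentation.

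What the objection does not remove is the contradiction in current text and the absence of any rule to resolve it.

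**Conclusion.** The point holds in a limited form: the Background and the Statistical Analysis contradict each other on whether the moderator question is primary, and nothing elsewhere decides between them. The 9.75% figure in step 3 applies only on the Statistical Analysis reading. It rests on a balanced layout, near-independence of the two tests and one interaction test. On the Background reading there is no inflation of the primary claim.

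This should be fixed before the data are analysed. It does not affect the data, the sample size or the estimate of the app effect; it affects which result may be called confirmatory.

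**What to change.** In the Statistical Analysis section:

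1. Call the app effect the primary aim (singular) and the moderator question the secondary aim, as the Background does.
2. State that Aim 1 on KOOS pain is the only primary test, at two-sided 5%. This also puts Aim 1's level into the analysis text.
3. State that the SF-12 and FFMQ-15 interaction tests, which come from the Objectives and Outcome Measures, are secondary and cannot by themselves make the trial positive. Both instruments need naming, because the Background's secondary aim mentions only quality of life.
4. Keep the sentence on analyses stratified by FFMQ-15 and SF-12, and label it as that same secondary analysis. Deleting it would remove the only mention of FFMQ-15 in that section.

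The cost is one paragraph of wording. The downside is that a positive interaction with a null Aim 1 is not a primary result.

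If the sponsor prefers to keep both aims primary, the price should be stated. Testing Aim 2 only after Aim 1 succeeds holds the error at 5%, but under the plan's own pattern the chance of claiming Aim 2 falls from about 80% to about 65%. Splitting alpha at 2.5% each leaves the interaction with 71.7% power at 72 per cell. Restoring 80% would take 87 per cell, which is 4 × 87 = 348 evaluable participants, or 348 / 0.75 = 464 enrolled at the plan's 25% dropout. Ranking Aim 2 as secondary avoids both costs.
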